 - 2. Reduction in kidney function (increase in creatinine or decrease in glomerular filtration rate)
 - 3. Very rarely causes dry cough
 - 4. Facial swelling (angioedema)

RN BP ASSESSMENT

- 1. RN BP Assessment Visit
 - a. Pre-Visit Planning: perform 1-2 weeks prior to appointment.
 - i. Call patient
 - 1. Request patient bring all pill bottles to appointment.
 - 2. If patient has home blood pressure device, ask patient to bring home device and written home blood pressure log (after checking blood pressure twice daily for 1 week) to appointment.
 - ii. GFR Assessment
 - 1. Review prior labs in "Results Review".
 - 2. Review last potassium, creatinine and glomerular filtration rate (GFR) in last 6 months.
 - 3. If all present within 6 months, no further action needed for GFR assessment.
 - 4. If no creatinine and GFR in last 6 months, order "CREATININE with-GFR".
 - 5. If no potassium in last 6 months, "POTASSIUM LEVEL".
 - 6. Compare most recent GFR with second most recent GFR. If most recent GFR is > 20% lower, discuss with provider.
 - 7. If GFR < 60 but >/= 30, update problem list to include "CKD Stage 3"
 - 8. If GFR < 30 but >15, update problem list to include "CKD Stage 4".
 - 9. If GFR < 15, update problem list to include "CKD Stage 5"
 - iii. Proteinuria Assessment
 - 1. Review prior urine protein testing in "Results Review" for following results in last 1 year:
 - a. Microalbumin/Creatinine Ratio, Urine, Random
 - b. Protein, Urine and Creatinine, Urine (both are required as ratio must be calculated manually by dividing urine

- protein by urine creatinine).
- c. Protein, 24 hour, Urine
- d. Urine dipstick protein (adjusted for specific gravity)
- 2. If labs are present in last year, no further action is needed for Proteinuria Assessment.
- 3. If none are available, order MICROALBUMIN/CREATININE RATIO

NOTE: "Unable to calculate" for Microalbumin/Creatinine Ratio implies zero protein present in urine.

- b. Assessment of BP goal
Goal blood pressure is SBP < 140 mmHg AND DBP < 90 mmHg.
- c. Provide education annually on non-pharmacologic management of hypertension.
 - i. Low Sodium Diet
 - 1. Discuss with patient importance of low sodium diet included no added salt as well as checking labels for processed foods.
 - 2. Provide patient with Exit Care SmartText in Patient Instructions: DIET-2 GRAM LOW SODIUM (choose appropriate language).
 - 3. Refer to nutrition at same clinical site for further counseling as needed.

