Do not start new patients on metformin	
▪ eGFR <30	Stop metformin
- May cause GI side effects, including diarrhea and cramping, but these are minimized if started at low doses, taken with food, and titrated up slowly
 - Start at 500 mg once to twice daily with meals
 - Wait 1-2 weeks before increasing dose
 - If GI side effects occur, reduce dose to the dose last tolerated
 - Maximal dose is 2550 mg/day in divided doses or 2000 mg of the extended release (ER) formulation
- Prolonged use is associated with vitamin B12 deficiency

Sulfonylureas (glyburide, glipizide, glimepiride)

- Promote insulin secretion independent of ambient glucose level
 - Risk of hypoglycemia
 - Use with caution in the elderly and in CKD
 - **Avoid use in stage 3 or greater CKD**
 - Glipizide is preferred in CKD
- Efficacy is good initially but requires addition of second agent sooner than other drugs
- Risk for weight gain
- Must not skip or delay meals
- Low cost

Rapid-acting Secretagogues (repaglinide, nateglinide)

- This class, the metaglinides, are more rapid-acting than sulfonylureas and are taken before each meal
- May cause less hypoglycemia than sulfonylureas in patients who skip or delay meals
- Expensive

Pioglitazone

- Promotes insulin sensitivity in muscle and reduces hepatic glucose production
- Disadvantages include weight gain (both water and fat), edema and heart failure, and increased risk of bone fracture
- Contraindicated in NYHA Class III and IV heart failure
- Advantages include low risk of hypoglycemia and good durability of efficacy
- Generic formulation now available; low cost
- No adjustment for eGFR

DPP-4 Inhibitors (sitagliptin, saxagliptin, linagliptin, alogliptin)

- Increase glucose-dependent insulin secretion and decrease glucagon secretion
- Low risk of hypoglycemia; no weight gain
- Expensive
- Possible risk of acute pancreatitis
- Possible increased risk of heart failure admissions

SGLT2 Inhibitors (canagliflozin, dapagliflozin, empagliflozin)

- Inhibit reabsorption of glucose in the kidney, thereby promoting glucosuria
- Advantages include low risk of hypoglycemia, weight loss, and blood pressure lowering
- Do not rely on intact beta cell function, so SGLT2 inhibitors are effective at all stages in the natural history of type 2 diabetes
- Do rely on renal function; as renal function falls, SGLT2 inhibitors are less effective
- When starting, consider reducing doses of diuretics or other antihypertensives to avoid hypotension

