- Must use with caution or not at all in patients with eGFR <60;
- Renal dosing:
 - For canagliflozin and dapagliflozin see Table below
 - Empagliflozin: do not use for eGFR <45

GLP-1 Receptor Agonists (exenatide, liraglutide, albiglutide)

- Stimulate glucose-dependent insulin secretion, decrease glucagon secretion, delay gastric emptying, and diminish appetite
- Advantages include low risk of hypoglycemia and weight loss
- Disadvantages include requiring injection and cost
- Some experience nausea/vomiting, especially soon after starting treatment
- Rodents have developed thyroid C-cell tumors in these drugs, but the risk for humans is not known
- Contraindicated in patients with personal or family history of medullary carcinoma of the thyroid or multiple endocrine neoplasia syndrome type 2
- Some reports of exenatide drug-induced renal injury

Protocol Table 2

Table 3—Recommended dose adjustments for noninsulin antihyperglycemic agents in DKD

Medication	In patients with impaired GFR	In dialysis patients
Biguanides		
Metformin	U.S. prescribing information states “do not use if serum creatinine ≥ 1.5 mg/dL in men, ≥ 1.4 mg/dL in women” British National Formulary and the Japanese Society of Nephrology recommend cessation if eGFR <30 mL/min/1.73 m ²	Contraindicated
Second-generation sulfonylureas		
Glipizide	No dose adjustment required	No dose adjustment required
Glimepiride	Initiate conservatively at 1 mg daily	Initiate conservatively at 1 mg daily
Glyburide	Avoid use	Avoid use
Meglitinides		
Repaglinide	Initiate conservatively at 0.5 mg with meals if eGFR <30 mL/min/1.73 m ²	No clear guidelines exist
Nateglinide	Initiate conservatively at 60 mg with meals if eGFR <30 mL/min/1.73 m ²	No clear guidelines exist
TZDs		
Pioglitazone	No dose adjustment required	15–30 mg daily has been used (190)
α-Glucosidase inhibitors		
Acarbose	Avoid if eGFR <30 mL/min/1.73 m ²	Avoid use
Miglitol	Avoid if eGFR <25 mL/min/1.73 m ²	Avoid use
GLP-1 receptor agonists		
Exenatide	Not recommended with eGFR <30 mL/min/1.73 m ²	Avoid use
Liraglutide	Not recommended with eGFR <60 mL/min/1.73 m ²	Manufacturer does not recommend use (currently under study)
Albiglutide	No dose adjustment required	No clear guidelines exist—limited clinical experience in severe impairment of kidney function
DPP-4 inhibitors		
Sitagliptin	100 mg daily if eGFR >50 mL/min/1.73 m ² 50 mg daily if eGFR 30–50 mL/min/1.73 m ² 25 mg daily if eGFR <30 mL/min/1.73 m ²	25 mg daily

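### Appendix II's class-wide instruction to avoid sulfonylureas in stage 3 or greater CKD conflicts with Protocol Table 2, which lists two of the three named drugs as usable with impaired GFR

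*Combined protocol and SAP*

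**What the plan says.** The sulfonylurea entry in Appendix II (under the specific guidelines for oral antidiabetes medications) has one heading that names glyburide, glipizide and glimepiride. Three of its bullets concern kidney disease:

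- a general caution, "Use with caution in the elderly and in CKD";
- a bold instruction, "Avoid use in stage 3 or greater CKD";
- directly after it, "Glipizide is preferred in CKD".

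The bold instruction exempts no drug. The caution and the glipizide bullet give no CKD stage.

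Protocol Table 2, later in the same appendix, has a column headed "In patients with impaired GFR" and another for dialysis patients. In both columns glipizide reads "No dose adjustment required", glimepiride reads "Initiate conservatively at 1 mg daily", and glyburide alone is marked as a drug to avoid.

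Section 6.5 makes Appendix II the detailed diabetes and lipid protocol of the intervention, which primary care practitioners may choose to initiate through smart sets.

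**The concern.** A practitioner treating an intervention patient with an eGFR of, say, 45 finds two answers on glipizide and two on glimepiride in the same appendix. Two practices could handle the same patient differently and both claim to follow the protocol.

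The subject is not incidental. Appendix II states that the risk of hypoglycemia rises as eGFR falls below 60 and lists hypoglycemia as a risk of this class. Section 2.3 includes hypoglycemia among the intervention-group events reported quarterly to the DSMB. Section 9.1 captures it whether or not it leads to admission, and Section 3.2.2 counts it among the disease-specific hospitalizations.

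Sections 9.1 and 10.1 also plan to monitor adherence to study procedures and protocol. Adherence on this item cannot be judged if using and avoiding the same drug both comply. Because practices are the randomized units, differing readings would also add between-practice variation to the intervention as delivered.

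**Working it through.** The plan states no figure on this point, so the check is a comparison of texts, followed by a bound on reach.

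**Step 1: drug by drug, for stage 3 or greater CKD.**

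| Drug | Class text | Table 2, impaired GFR | Table 2, dialysis | Agree? |
|---|---|---|---|---|
| Glyburide | avoid | avoid | avoid | yes |
| Glipizide | avoid; also preferred in CKD, no stage given | no adjustment | no adjustment | no |
| Glimepiride | avoid | starting instruction | same starting instruction | no |

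Two of three drugs conflict.

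**Step 2: can the conflict be read away by stage?** Appendix I fixes the meaning of stage 3: "If GFR < 60 but >/= 30, update problem list to include" CKD stage 3. Stage 4 lies below 30, and stage 5 below 15.

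- The glipizide bullet can be reconciled with the avoid line. It could refer to CKD below stage 3, that is, albuminuria with eGFR of 60 or more. It is the weaker part of the conflict.
- The table cannot be reconciled in this way. Some other rows under the impaired-GFR column (alogliptin, canagliflozin) do include eGFR values of 60 or above, but those rows state their cut-offs. The sulfonylurea rows state none, so they cover the whole impaired range, and the dialysis column repeats the glipizide and glimepiride entries for the most severe disease.

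**Step 3: is stage 3 or greater within the trial?** Section 5.1.1 admits patients by two or more eGFRs below 60, or by two or more positive tests for albuminuria or proteinuria. Section 5.2 withholds the model from stage 5. Stages 3 and 4 therefore remain, alongside patients with eGFR of 60 or more who enter through the urine tests.

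**Step 4: how many patients?** Let

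exposed = N × a × s × u,

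where N = 10,991 (Section 4), a is the share in the intervention arm, s the share of that arm at stage 3 or 4, and u the share of those for whom a sulfonylurea is used or considered under the protocol. The documents give none of a, s or u. I assume a = 0.5, since there are two groups with permuted blocks but no stated ratio. Then N × a = 10,991 / 2 = 5,495.5, about 5,496. Setting u = 1 gives an upper bound for each s:

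| s | 5,496 × s | Share of all 10,991 |
|---|---|---|
| 25% | 1,374 | 12.5% |
| 50% | 2,748 | 25% |
| 75% | 4,122 | 37.5% |
| 100% | 5,496 | 50% |

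Under equal allocation the conflict cannot reach more than about half of the study patients. Any u below 1 reduces these counts in proportion.

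**The case against.** The strongest reply is that Appendix II is guidance, not a mandate. It is meant to assist practitioners, its activation is optional (Section 6.5), and primary care providers make the final decisions in both groups (Section 9.1). Section 5.2 lets them withhold the intervention from any patient. Some variation between practices is expected in a pragmatic trial. This stands, and it limits the harm. It does not make the guidance coherent, because discretion lets a provider depart from advice but does not say what the advice is.

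A second reply is that Table 2 is reproduced from a published report and answers a dosing question rather than directing use. On this view the appendix merely sets sources side by side, as it does for metformin. That is fair as far as it goes. For metformin, however, the text tells the reader that the label restriction has been questioned; for sulfonylureas it signals no disagreement. The appendix also treats the table as operative, because its SGLT2 inhibitor entry sends the reader there for renal dosing. And the table does mark drugs to avoid, glyburide among them, so it speaks to use as well as dose.

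Three stronger readings are tempting but unsupported:

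- *Most study patients, or every intervention patient enrolled through eGFR below 60, face opposite instructions.* No eGFR split is given, entry by urine tests alone is possible, controls receive usual care (Section 2.3), stage 5 is excluded from the model, and the point matters only where a sulfonylurea is in play.
- *The conflict is built into the electronic tools.* The readable text shows no sulfonylurea rule in any smart set, and the smart-set figure is not available.
- *Trial results are compromised.* Nothing in the documents shows an effect on the primary outcome. Hypoglycemia has other safeguards: Appendix II has patients asked about it at each visit and raises glycemic targets when it is frequent or dangerous.

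**Conclusion.** The inconsistency holds. The class-level line and Protocol Table 2 disagree on glipizide and glimepiride, and no statement gives one precedence. The unstaged glipizide bullet adds ambiguity but would not establish the conflict alone.

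The reach is intervention-arm patients with stage 3 or 4 CKD for whom a sulfonylurea is used or considered. Their number cannot be derived from the documents. The ceiling of about half of all study patients rests on assumed equal allocation and on extreme values for the two unknown shares. The consequence is for clarity of the intervention, assessment of fidelity and interpretation of hypoglycemia events. Sample size, alpha and the primary analysis do not depend on it. It merits correction because the conflict lies in the trial's own intervention guidance, on a monitored safety matter.

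**What to change.** The sponsor should reconcile the sulfonylurea bullets in Appendix II with Protocol Table 2, so that text and table give consistent guidance for each named drug in stage 3 and stage 4 CKD. If the table is kept as published, a line should say whether the text or the table governs. The glipizide bullet should state the CKD stages it covers. The Diabetes Advisory Workgroup, listed in the contents as Section 16.2.3, is a natural owner. This review does not say which instruction is right.

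The sponsor should also check whether any smart set or training material built from Appendix II carries the conflict, and correct it if so.

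The cost is an appendix edit, submitted to the IRBs as Section 14.2 requires, plus a check of the electronic tools. No change to the design, sample size or analysis is needed.
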